#### **4.6 Ethno-Bridging Data from a Study of Healthy Japanese and Caucasian Volunteers**

Study AKB-6548-CI-0020 was a randomized, double-blind, placebo-controlled, dose escalation study conducted at a single clinical site in the United States. The study was conducted to compare the pharmacokinetics (PK) and PD of vadadustat in healthy adult male and female volunteers of Japanese and Caucasian descent.

#### **Brief Overview of Study Design**

The primary study entry criteria included male or female subjects between 20 and 55 years of age, with a body mass index of 18-30 kg/m^2, and a body weight of 45-90 kg for Japanese subjects and a body weight of 50-100 kg for Caucasian subjects. For study eligibility, the Caucasian subjects had to be Caucasian of European or Latin American descent. The Japanese subjects had to fulfill the following eligibility criteria: Must have been born in Japan; must have had 2 biological Japanese parents and 4 Japanese grandparents as confirmed by interview; must have been living outside of Japan for up to 10 years at the time of the screening visit; and the subject's lifestyle, including diet, must not have changed significantly since leaving Japan.

[figure not shown]
Eligible subjects were enrolled into one of 3 dose cohorts: 150, 300, or 600 mg daily oral doses of vadadustat (or placebo). Subjects received daily doses of study drug (either vadadustat or placebo) for 10 days. Each of the 3 dose cohorts enrolled 8 Japanese and 8 Caucasian subjects.

Within each dose cohort assignment, subjects were randomized at a 3:1 ratio to receive either vadadustat (n=6) or placebo (n=2).

### Brief Overview of Study Results

Based on the study results, the PK and PD of vadadustat are similar in healthy Caucasian and Japanese subjects with no ethnic factors identified. The mean plasma concentration versus time plot for vadadustat is shown in Figure 2. Although there is a slight increase in the EPO exposure in Japanese subjects at the highest dose (600 mg); this increase is not clinically meaningful. The mean reticulocyte concentrations in subjects of both ethnicities is also similar. EPO levels following vadadustat dosing were within normal physiologic range, at a concentration below EPO receptor saturation, and substantially lower than EPO levels following ESA dosing. Vadadustat was generally well-tolerated in this study.

**Figure 2 Mean ( $\pm$  Standard Error) Plasma Concentration versus Time Profiles Following Administration of a Repeated Once Daily Oral Dose of Vadadustat to Healthy Caucasian and Japanese Subjects on Day 10 (Study AKB-6548-CI-0020)**

#### **4.7 Potential Benefits and Risks**

*Please see the vadadustat Investigator's Brochure for additional discussion and information for the following section.*

Vadadustat offers the potential of flexible oral dosing that is easier to adjust than injectable hormone ESAs. This alternate therapeutic approach may avoid the excursions and fluctuations in Hb levels seen with currently available injectable ESAs and provide for a controlled, steady rise in Hb concentration. This less aggressive approach to modifying the Hb concentration may be of benefit based on suggestion from the US Food and Drug Administration (FDA) that fluctuations in Hb concentrations, rapidly increasing Hb levels, and excursions above the target level are associated with an increased risk of CV events ([Unger 2010](#)).

In addition, HIF activation is associated with increased expression of ferroportin and transferrin and decreased expression of hepcidin ([Liu 2012](#), [Peysonnaux 2007](#), [Tacchini 1999](#)). These changes in iron biomarkers are consistent with enhanced iron mobilization and utilization to promote Hb synthesis and erythropoiesis. In the Phase 1b multiple ascending dose study, a prominent effect on iron metabolism was noted with the dosing of vadadustat, including a rapid increase in iron uptake, a dose responsive increase in TIBC, decreases in hepcidin and ferritin, and an increase in transferrin. A similar pattern was observed in the Phase 2a and 2b studies, with dose responsive increases in TIBC and decreases in ferritin and hepcidin.

To date, the acute findings observed at doses less than the maximum tolerated dose (MTD) in animals have been shown to be reversible and dose-related. In addition, most of the findings have followed a pattern that would have been predicted based on the known HIF and HIFPH biochemistry, pharmacology, and human genetic variations (eg, Chuvash polycythemia). In the completed clinical studies, vadadustat has been generally well-tolerated.

### **5 STUDY OBJECTIVES AND ENDPOINTS**

Note that a pre-treatment value for Hb is defined as the average of 2 values obtained prior to treatment, ie, the qualifying screening value and the baseline value.

#### **5.1 Primary Objective and Endpoint**

The primary objective of this study is to assess the dose-response relationship between oral vadadustat once daily dosing for 6 weeks and the change in Hb in Japanese subjects with anemia secondary to NDD-CKD; this is to define the starting dose for use in Phase 3 clinical studies in Japan.

The primary endpoint that will be used to assess this objective is the mean change in Hb levels from pre-treatment to the end of the primary efficacy period (Week 6).

#### **5.2 Secondary Objectives and Endpoints**

The secondary objectives of this study are:

- To assess the safety, tolerability, pharmacokinetics (PK), and pharmacodynamics (PD) of oral vadadustat once daily dosing in Japanese subjects with anemia secondary to NDD-CKD during the 6-week, primary efficacy period
- To evaluate the effect of dose adjustments and demonstrate the maintenance effect on Hb during a 10-week dose adjustment and maintenance period

- To assess the time to reach the target Hb range from baseline

The efficacy endpoints that will be used to assess these objectives include the following:

- Time to reach target Hb level of 10.0-12.0 g/dL from baseline
- Mean Hb levels at the end of the primary efficacy period (Week 6) and at the end of the dose adjustment and maintenance period (Week 16)
- Proportion of subjects who achieve target Hb 10-12 g/dL at the end of the dose adjustment and maintenance period (Week 16)
- Mean change in Hb between pre-treatment and the end of the dose adjustment and maintenance period (Week 16)
- Mean change in hematocrit, RBC count, and reticulocyte count from baseline to the end of the primary efficacy period (Week 6) and the end of the dose adjustment and maintenance period (Week 16)
- Mean change in iron indices (ie, iron, total iron-binding capacity [TIBC], TSAT, and ferritin) and hepcidin from baseline to the end of the primary efficacy period (Week 6) and the end of the dose adjustment and maintenance period (Week 16)
- Proportion of subjects requiring rescue with RBC transfusion from baseline to the end of the primary efficacy period (Week 6) and the end of the dose adjustment and maintenance period (Week 16)
- Proportion of subjects requiring rescue with ESAs from baseline to the end of the primary efficacy period (Week 6) and the end of the dose adjustment and maintenance period (Week 16)
- Number of dose adjustments from baseline to the end of the dose adjustment and maintenance period (Week 16)
- Maintenance of iron sufficiency (defined as ferritin  $\geq$ 50 ng/mL and TSAT  $\geq$ 20%) from baseline to the end of the primary efficacy period (Week 6) and the end of the dose adjustment and maintenance period (Week 16)
- Plasma concentration profile of vadadustat and its metabolites using pre-dose sample from Week 4

The safety endpoints that will be used to assess these objectives include the following:

- Safety assessments, including adverse events, vital signs, electrocardiograms (ECGs), and other laboratory assay results (eg, chemistry, components of the complete blood count [CBC] other than the ones noted above, and vascular endothelial growth factor [VEGF])

## 6 STUDY DESIGN

[figure not shown]
### 6.1 Study Design

This is a Phase 2, randomized, double-blind, placebo-controlled, dose-finding study to assess the efficacy, safety, tolerability, PK, and PD of orally administered vadadustat in Japanese subjects with anemia secondary to NDD-CKD.

The study has a planned enrollment of 48 subjects to be enrolled at approximately 25 sites in Japan. There will be 16 subjects in each of the 3 tablet-count groups.

An overview of the study design is presented in Figure 3.

**Figure 3: Overview of Study Design**

\* For subjects who develop an excess Hb response during the primary efficacy period, the number of tablets of study drug will be decreased (see Section 8.2.4). For these subjects, the number of tablets of vadadustat initiated at the Week 6 visit will be lower than indicated.

The study will include the following periods:

- Eligibility screening period (up to 4 weeks)
- Primary efficacy period (6 weeks; Weeks 1 to 6)
- Dose adjustment and maintenance period (10 weeks; Weeks 7 to 16)
- Follow-up period (2 weeks; Weeks 17 and 18)

Subjects will participate in a screening period (4 days to 4 weeks) to determine study eligibility, and eligible subjects will be randomized following the screening period.

Using a central randomization system, subjects will be randomized 1:1:1 to receive 1, 2, or 4 tablets at their baseline visit (Day 1). Within each tablet-count group, subjects will be randomized 3:1 to receive vadadustat (150, 300, or 600 mg vadadustat) or placebo. See [Section 8.2.2](#) for information regarding the randomization scheme.

Study drug treatment will be administered during a 6-week primary efficacy period. See [Section 8.2.4](#) for information on study drug administration. The primary efficacy period includes fixed-dose treatment to establish a dose-response relationship. However, if Hb level increases rapidly or if the Hb level exceeds 13.0 g/dL, the study drug dose can be decreased or interrupted (see [Section 8.2.4](#)).

After completing the primary efficacy period, subjects will continue to a 10-week dose adjustment and maintenance period (see [Section 8.2.5](#)). Subjects receiving placebo will be switched to vadadustat, and study drug dose will be adjusted to achieve a target Hb of 10.0-12.0 g/dL based on dose adjustment guidelines (see [Section 8.2.5](#)).

Vadadustat treatment will stop after the dose adjustment and maintenance period has been completed (Week 16) and subjects will continue in a 2-week follow-up period (Week 17-18).

The clinical and safety assessments will be performed as described in [Section 9.4](#) and as listed in [Appendix A](#).

## 6.2 Study Duration

Individual subjects will participate in the study for up to 22 weeks, including the eligibility screening period (up to 4 weeks), primary efficacy period (6 weeks), dose adjustment and maintenance period (10 weeks), and follow-up period (2 weeks).

[figure not shown]
Note: Subjects who discontinue prematurely from the study or permanently discontinue study drug will complete the end-of-treatment (Week 16) visit followed in two weeks by the Week 18 visit (see [Section 7.6.3](#)).

## 6.3 Rationale for Study Design

The study design of this randomized, double-blind, placebo-controlled, dose-finding study in Japanese subjects with anemia secondary to NDD-CKD is modeled on a previously completed dose-finding study in subjects with anemia secondary to NDD-CKD that included mostly Caucasian and Black/African American subjects (Study AKB-6548-CI-0005).

A treatment duration of 6 weeks will be adequate to demonstrate the dose-response relationship of vadadustat with change in Hb, as 6 weeks of treatment with vadadustat in Study AKB-6548-CI-0005 was adequate to establish a statistically significant dose-response relationship (as shown in [Figure 4](#)). An additional 10-week dose adjustment and maintenance period will be conducted to evaluate the effect of dose adjustments and demonstrate the maintenance effect on Hb.

**Figure 4: Absolute Change in Hemoglobin ( $\pm$  Standard Error of Mean, g/dL) at Week 6 Compared to Baseline (Study AKB-6548-CI-0005)**

Note: 25% of the subjects in the 630 mg vadadustat treatment group and 10% of subjects in the 500 mg vadadustat treatment group had their doses reduced by Week 4.

Note: Two tailed paired t-test of hemoglobin, baseline versus Week 6, p <0.01

## 6.4 Dose Justification

The doses to be used in the present study (150, 300, and 600 mg once daily) were previously evaluated in the ethno-bridging study (Study AKB-6548-CI-0020). The results from Study AKB-6548-CI-0020 showed that the doses are generally well tolerated, and similar PK and PD responses to vadadustat were demonstrated between the Caucasian and Japanese healthy subjects.

Furthermore, the same dose range of 150 mg to 600 mg was previously tested in US-based studies enrolling more than 200 subjects with either NDD-CKD (Phase 2 studies AKB-6548-CI-0005 and AKB-6548-CI-0007) or DD-CKD (Phase 2 study AKB-6548-CI-0011). In these completed studies, the dose range of 150-600 mg was shown to be generally well-tolerated, and efficacious in raising and/or maintaining Hb at the desired target level in patients with anemia secondary to NDD-CKD or DD-CKD. Importantly, the dose range provides great flexibility in enabling adjustment of vadadustat dose according to an individual patient's Hb response. The product labeling for NESPO® and ESPO® in Japan also allow for adjustable dosing based on Hb response in individual patients.

## 7 SELECTION AND WITHDRAWAL OF SUBJECTS

### 7.1 General Criteria

The study population will consist of male and female Japanese adults aged 20 years or older with anemia secondary to NDD-CKD who are not currently being treated with an ESA.

To be eligible for this study, a subject or their legally acceptable representative must have provided valid informed consent and must meet the following criteria. No study procedures (including screening tests) may be performed until after the informed consent has been legally signed.

## 7.2 Inclusion Criteria

Subjects must meet the following inclusion criteria to be eligible for study participation:

1. Male and female Japanese subjects, aged 20 years or older
2. Diagnosis of CKD based on an estimated glomerular filtration rate (eGFR) of  $\leq 60$  mL/min/1.73 m^2 (using the 2009 Japanese Society of Nephrology equation; [Matsuo 2009](#))
3. Not currently being treated with dialysis and not expected to start dialysis within 3 months of screening
4. Hemoglobin (Hb)  $\leq 10.5$  g/dL during screening
5. Serum ferritin  $\geq 50$  ng/mL during screening
6. TSAT  $\geq 20\%$  during screening
7. Folate and vitamin B12 greater than or equal to the lower limit of normal during screening
8. For subjects who are receiving oral iron supplementation, the dose of oral iron supplementation must be stable for at least 28 days prior to the screening period. For subjects who are not receiving oral iron supplementation, no iron supplementation may have been ingested for at least 28 days prior to the screening period.
9. Understands the procedures and requirements of the study and provides written informed consent and authorization for protected health information disclosure

## 7.3 Exclusion Criteria

Subjects who meet any of the following exclusion criteria will not qualify for study participation:

1. Anemia due to a cause other than CKD or presence of active bleeding or recent blood loss
2. Sickle cell disease, myelodysplastic syndromes, bone marrow fibrosis, hematologic malignancy, myeloma, hemolytic anemia, thalassemia, or pure red cell aplasia
3. RBC transfusion within 4 weeks prior to or during screening
4. Intravenous iron within 4 weeks prior to or during screening

5. Any ESA use within 6 weeks prior to or during screening (eg, recombinant human erythropoietin, darbepoetin alfa, or methoxy polyethylene glycol-epoetin beta)
6. Aspartate aminotransferase (AST)/serum glutamic oxaloacetic transaminase (SGOT), alanine aminotransferase (ALT)/serum glutamic pyruvic transaminase (SGPT), or total bilirubin  $>2.0 \times$  upper limit of normal during screening. A history of Gilbert's syndrome is not an exclusion criterion.
7. Uncontrolled hypertension (confirmed diastolic blood pressure  $>110$  mm Hg or systolic blood pressure  $>180$  mm Hg) during screening
8. Body mass index (BMI)  $>42.0 \text{ kg/m}^2$
9. Severe heart failure during screening (New York Heart Association Class III or IV)
10. History of untreated proliferative diabetic retinopathy, diabetic macular edema, age-related macular degeneration, central retinal vein occlusion, active retinal hemorrhage, or ongoing ocular treatment with laser photocoagulation or anti-VEGF therapies
11. Acute coronary syndrome (hospitalization for unstable angina or myocardial infarction), surgical or percutaneous intervention for coronary, cerebrovascular, or peripheral artery disease (aortic or lower extremity), surgical or percutaneous valvular replacement or repair, sustained ventricular tachycardia, hospitalization for heart failure, or stroke within 12 weeks prior to or during screening
12. History of active malignancy within 2 years prior to or during screening, except for treated basal cell carcinoma of skin, curatively resected squamous cell carcinoma of skin, cervical carcinoma in situ, or resected benign colonic polyps
13. History of deep vein thrombosis (DVT) or pulmonary embolism (PE) requiring active treatment within 8 weeks prior to or during screening
14. History of hemosiderosis or hemochromatosis
15. History of prior organ transplantation or scheduled organ transplant (subjects on kidney transplant wait-list are not excluded), or prior hematopoietic stem cell or bone marrow transplant (corneal transplants and stem cell therapy for knee arthritis are not excluded)
16. Use of an investigational medication or participation in an investigational study within 30 days or 5 half-lives of the investigational medication (whichever is longer), prior to screening
17. Previous participation in a study with a hypoxia-inducible factor prolyl-hydroxylase inhibitor, other than vadadustat, within 90 days prior to screening
18. Hypersensitivity to vadadustat, or to any of its excipients

19. Females who are pregnant or breast-feeding
20. Females of childbearing potential who are unable or unwilling to use an acceptable method of contraception
21. Non-vasectomized males who are unable or unwilling to use an acceptable method of contraception
22. Any other reason that in the opinion of the investigator would make the subject not suitable for participation in the study

## 7.4 Retesting and Rescreening

### 7.4.1 Retesting

All screening laboratory tests, including any repeat measurements, must be performed within the screening window.

The screening period can last up to 4 weeks long, with a minimum of 4 days between the last qualifying repeat measurement and the baseline visit (Day 1), ie, the screening period window is from Day -28 to Day -4.

Subjects who initially fail to qualify for the study based on laboratory test results may have their laboratory value retested once within the screening period, at the investigator's discretion.

For eligibility purposes, if the Hb measured at the screening visit is  $>10.5$  g/dL and  $<11.0$  g/dL, Hb level can be retested once at the investigator's discretion. The subject should not be retested if the Hb level measured at the screening visit is  $\geq 11.0$  g/dL.

Retesting within the screening period does not constitute rescreening; however, if retesting falls outside of the screening period, it should be considered a rescreen (see Section 7.4.2).

### 7.4.2 Rescreening

Subjects who fail to meet the qualifying criteria for Hb or eGFR during screening may be considered for rescreening at the discretion of the investigator, if it is felt that the subject's status has changed and that the subject may now qualify for the study. Additionally, subjects who fail to qualify for the study based on low ferritin, TSAT, folate, or vitamin B12 values may be considered for rescreening after receiving replacement therapy.

If intravenous (IV) iron is used to replete iron stores, the last dose of IV iron must be administered at least 4 weeks prior to rescreening.

Screening is limited to 3 attempts (during the initial screening and 2 additional rescreening attempts). Subjects who fail to qualify for the study at the initial screening visit will receive a new subject number for each rescreening attempt. If rescreened, the subject will also sign a new informed consent form and will repeat all screening procedures for each rescreening attempt.

## **7.5 Study Completion, Study Termination, and Individual Study Site Termination**

### **7.5.1 Study Completion**

The study will be considered completed after all enrolled subjects have completed study participation, and the adverse event (AE) reporting period has been completed for each enrolled subject (see [Section 10.3.1](#) for information regarding the AE reporting period).

### **7.5.2 Study Termination**

The entire study may be suspended or terminated by the sponsor for safety or other unanticipated reasons or upon request of regulatory agencies. Criteria for premature study termination or suspension are detailed in [Section 14.1](#).

### **7.5.3 Individual Study Site Termination**

Study participation may be suspended or terminated at an individual investigational site for various reasons. Criteria and procedures for premature termination or suspension of an investigational site are detailed in [Section 14.2](#) and [Section 14.3](#).

## **7.6 Subject Completion and Individual Subject Discontinuation**

### **7.6.1 Subject Completion**

A subject will be considered as having completed the study after completing participation in the Week 18 visit (end of the 2-week follow-up period).

Note: Subjects who discontinue prematurely from the study or permanently discontinue study medication will complete the end-of-treatment (Week 16) visit followed in two weeks by the Week 18 visit (see Section 7.6.3).

See [Section 10.3.6](#) for information regarding follow-up of unresolved events.

### **7.6.2 Conditions and Documentation of Individual Subject Study Drug Discontinuation**

Subjects will discontinue study medication for any of the following conditions:

- Completion of the protocol-defined dosing period (see [Appendix A](#))
- Worsening of anemia requiring ESA rescue or blood transfusion
- Unacceptable toxicity or drug intolerance
- Investigator discretion
- Subject withdrawal of consent
- Subject becomes pregnant
- Other reasons

The investigator must document the primary reason for discontinuation in the appropriate case report form (CRF).

### **7.6.3 Individual Subject Discontinuation**

Subjects permanently discontinuing study medication or withdrawing early from the study prior to the Week 16 visit should complete the Week 16 (end-of-treatment) clinical and laboratory assessments within 1 day of stopping study medication, if possible. Such subjects should also

complete the 2-week follow-up period and complete the Week 18 visit assessments (see [Appendix A](#)). For subjects who discontinue study medication, the investigator should resume standard of care treatment, as deemed appropriate.

If a subject does not return for a scheduled visit, every effort should be made to contact the subject.

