#### **4.2 Available Therapies for Anemia in Patients with CKD**

Erythropoiesis-stimulating agent (ESAs), including epoetin alfa and darbepoetin alfa administered either intravenously or subcutaneously, along with iron therapy are currently the standard of care for treating anemia in patients with CKD. Treatment with exogenous recombinant ESAs can raise Hb, relieve symptoms, and reduce the complications of anemia including avoiding RBC transfusions which carry the risks of infection, iron overload, and impact candidacy for kidney transplantation.

Several large prospective randomized controlled trials in patients with CKD (GFR categories G3a to G5) have suggested an increased risk of death and cardiovascular (CV) events when targeting higher Hb levels ([Besarab 1998](#), [Drueke 2006](#), [Pfeffer 2009a](#), [Pfeffer 2009b](#), [Singh 2006](#)). Additional analyses suggest that the ESAs themselves may be causative of the increased events and not the Hb level, and is supported by studies in CKD patients on dialysis with naturally occurring higher Hb levels and no increase in CV events ([Solomon 2010](#), [Szczech 2008](#), [Goodkin 2011](#)). The risks identified with ESAs from these trials have led to changes in prescribing information and clinical practice guidelines in the USA and Europe.

In the USA, the mortality and CV risks associated with ESAs are outlined in a black-box warning in the prescribing information of ESAs with a recommendation to use the lowest dose possible to avoid transfusions.

The European Union (EU) Summary of Product Characteristics (SmPC) for ESAs suggests caution with the use of ESAs with a recommendation to keep Hb levels between 10-12 g/dL. Furthermore, recent clinical practice guidelines ([Locatelli 2013](#)) recommended that risk factors for stroke (including a past history of stroke) and the presence of active malignancy or a past history of malignancy should be taken into account when making treatment decisions to use ESAs for the treatment of anemia.

Although the CV risk is lower in Japanese subjects compared with Caucasian subjects, guidelines from the Japanese Society of Nephrology ([JSN 2014](#)) stated that ESA treatment targeting Hb levels 12–13 g/dL did not seem to be effective for preventing CKD progression or decreasing the incidence of CV disease compared to the Hb level of 9–11.5 g/dL, but rather had the potential to lead to an increase in the incidence of CV disease.

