#### **8.4.2 ESAs, Intravenous Iron, and Blood Transfusion**

Subjects may not receive any ESA treatment within 6 weeks prior to the screening period and through the follow-up period (eg, recombinant human erythropoietin, darbepoetin alfa, or methoxy polyethylene glycol-epoetin beta). See [Section 8.2.6](#) for the rescue therapy guidelines.

Subjects may not receive intravenous iron or blood transfusion within 4 weeks prior to the screening period and through the follow-up period. Use of intravenous iron supplementation after Day 1 will be considered a protocol deviation but will not be considered a reason for subject discontinuation.

ESAs and RBC transfusions are allowed as rescue therapies, please refer to Section 8.2.6 for the rescue therapy guidelines. Note that subjects who initiate rescue therapy will be required to stop study drug treatment and will be discontinued from the study (see [Section 7.6.3](#)).

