#### **9.4.8 Week 18 Follow-Up Visit (or 2 weeks after end-of-treatment follow-up visit)**

For subjects who complete the dose adjustment and maintenance period, the follow-up visit will be conducted 2 weeks after their end-of-treatment visit (Week 16).

For subjects who discontinue the study prematurely (ie, prior to Week 16), the follow-up visit will be conducted 2 weeks after their end-of-treatment visit.

At the follow-up visit, the following activities/procedures will be performed:

- Vital signs (heart rate and blood pressure should be assessed in a seated position after 5 minutes of rest and prior to blood draws)
- AE review (see [Section 10.3.6](#) for follow-up of unresolved events)
- Rescue therapy (ESA rescue and RBC transfusion) review
- Concomitant medication review
- Laboratory procedures:
  - CBC
  - Chemistry and eGFR

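### Section 7.6.3 has investigators resume standard of care once study drug stops, while Section 8.4.2 bars ESA and IV iron until follow-up ends, with no exception for subjects off study drug

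*Protocol*

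**What the plan says.** References are to the latest protocol version in the file, the one whose primary analysis is an ANCOVA with step-down testing.

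- **Section 7.6.3** covers subjects who stop study medication permanently, or withdraw, before Week 16. They have end-of-treatment assessments within 1 day of stopping, if possible, and should also "complete the 2-week follow-up period and complete the Week 18 visit assessments". It then adds: "For subjects who discontinue study medication, the investigator should resume standard of care treatment, as deemed appropriate".
- **Section 4.2** states that ESAs, "along with iron therapy are currently the standard of care for treating anemia in patients with CKD".
- **Section 8.4.2** states: "Subjects may not receive any ESA treatment within 6 weeks prior to the screening period and through the follow-up period". It also states: "Subjects may not receive intravenous iron or blood transfusion within 4 weeks prior to the screening period and through the follow-up period". ESAs and transfusion are allowed as rescue. IV iron after Day 1 is a protocol deviation, though not a ground for discontinuing the subject.
- **Section 8.2.6** allows ESA rescue on three conditions: the investigator judges it warranted, the anemia or its symptoms have deteriorated to a clinically significant degree, and Hb is confirmed below 9.0 g/dL. The investigator may proceed without the confirmatory Hb if the first two hold. Starting rescue obliges the subject to stop study drug.
- **Sections 9.3.1 and 9.4.8** carry the item "Rescue therapy (ESA rescue and RBC transfusion) review" from the first post-baseline visit through the follow-up visit.
- **Section 5.2** lists as a secondary endpoint "Proportion of subjects requiring rescue with ESAs from baseline to the end of the primary efficacy period (Week 6"), and likewise to Week 16.

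**The concern.** A site with a subject who stops study drug early, for example for intolerance, has two instructions for the next two weeks. One tells it to return to standard of care, which the protocol itself describes as ESA with iron. The other forbids ESA and IV iron until follow-up ends. Nothing in 8.4.2 limits the ban to subjects still on study drug, and nothing in 7.6.3 limits standard of care to treatments that 8.4.2 allows.

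Sites may settle this differently. The same action would then be a deviation by one section and compliance by the other. Hb, vital signs and adverse events at the follow-up visit would come from a mixture of subjects with and without ESA. The visit form asks about ESA under the label of rescue, and the protocol names no category for ESA given as ordinary care after study drug has stopped. Some of that use could therefore reach the rescue endpoint.

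**Working it through.** The protocol states no figure on this point to reproduce. The check is a comparison of texts, followed by two short calculations on timing and scale.

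**1. Do the instructions overlap?**

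| Question | 7.6.3 with 4.2 | 8.4.2 |
|---|---|---|
| Who? | Subjects off study drug before Week 16 | All subjects |
| When? | From stopping, with a 2-week follow-up still to run | Until follow-up ends |
| ESA? | Named within standard of care | Barred unless rescue |
| Iron? | Iron therapy named, route not given | IV iron barred; a deviation after Day 1 |
| Exception for subjects off study drug? | Not applicable | None |

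They overlap between the last dose and the follow-up visit. For ESA the conflict is direct. For IV iron it holds if standard-of-care iron therapy includes the intravenous route, which 4.2 does not exclude. Section 8.4.2 refers to 7.6.3, but only for subjects discontinued because of rescue, so the reference does not settle the matter. An earlier version in the file has the same pair of statements.

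**2. Does the rescue exception cover it?** Ordinary ESA after an intolerance stop does not by itself show the deterioration that 8.2.6 requires. Section 8.2.6 also makes stopping study drug a result of starting rescue, which presumes the subject is still taking it. IV iron has no rescue route.

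**3. Can such ESA fall inside an endpoint window?** Let *s* be the study day of stopping. End of treatment is within 1 day, and follow-up is 14 days later ± 3 days:

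- earliest follow-up visit = *s* + 14 − 3
- latest follow-up visit = *s* + 1 + 14 + 3

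| Stop day | Follow-up visit |
|---|---|
| 15 | Day 26 to 33 |
| 29 | Day 40 to 47 |
| 113 (planned end) | Day 124 to 131 |

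The Week 6 visit is Day 43 ± 3, that is Day 40 to 46. A subject who stops at Day 15 has the whole follow-up before Week 6. One who stops at Day 29 has follow-up ending at about Week 6. ESA started in that interval could fall in both the Week 6 and the Week 16 rescue windows. ESA started after a planned completion at Week 16 falls in neither.

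**4. Scale.** Section 11.2 plans 12 subjects per group.

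- One subject: 1/12 = 8.3 percentage points
- Two subjects: 2/12 = 16.7 percentage points

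These figures show how sensitive the proportion is. They do not estimate how many subjects would be affected.

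**The case against.** The best case against the point is that the wording gap is real but little follows from it.

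- **Classification.** Section 8.2.6 defines rescue, and routine ESA after an intolerance stop does not meet it. Section 7.6.2 requires the primary reason for stopping on the CRF and lists anemia needing rescue separately from intolerance. Section 9.3.1 records all medications through the final visit. Secondary endpoint analyses are left to the SAP, which is not shown. All this stands. The data needed to separate the two uses are largely collected, so a wrong entry is possible but not built in. An SAP cannot, however, tell a site which instruction to follow.
- **Discretion.** The 7.6.3 wording leaves treatment to judgement, 4.2 is background text, and subjects with ESA within 6 weeks of screening are excluded, so many have no recent ESA to resume. This reduces how often the conflict will arise. It does not lift the prohibition in 8.4.2.
- **Reach.** Some readers may infer that all 48 subjects are caught, because 7.6.2 lists "Completion of the protocol-defined dosing period" among the reasons for stopping. The instruction in 7.6.3 sits in a paragraph about stopping before Week 16, so extending it to completers strains the text.
- **Automatic rescue coding.** Some may also infer that ESA after any early stop will be recorded as rescue. No section says so.
- **Bias by arm.** Some may further infer that active arms will appear to need more rescue because intolerance is commoner there. The protocol gives no intolerance rates and describes vadadustat as generally well tolerated. Placebo subjects switch to vadadustat at Week 6, so the Week 16 proportions are not a clean contrast with placebo either.

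**Conclusion.** The contradiction holds in limited form. For a subject who stops early for a reason other than rescue, ESA or IV iron given as standard of care under 7.6.3 conflicts with 8.4.2 until the follow-up visit. Entry of such ESA as rescue is a risk created by the rescue-review item, not something the protocol prescribes.

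Deviation counts and the interpretability of follow-up Hb and safety data are affected. The ESA-rescue proportions may be affected, by 8.3 points per misclassified subject in a group of 12. The number of such subjects cannot be derived from the protocol, and no direction of bias between arms is shown. The primary endpoint is little affected, because end-of-treatment Hb is to be drawn within 1 day of stopping where possible. This assumes that a follow-up Hb taken after ESA is not used as the Week 6 value.

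The conclusion rests on reading standard of care in 7.6.3 in the sense given in 4.2. The protocol offers no other description of it.

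**What to change.** 1. Reconcile 7.6.3, 8.4.2 and 8.2.6 so that one statement governs ESA and IV iron between the last dose and the follow-up visit. Which clinical rule applies is for the sponsor to decide.
2. State that the rescue endpoints count only therapy started while on study drug or recorded as the reason for stopping it. The reason-for-discontinuation entry required by 7.6.2 already supports this.
3. Record ESA, IV iron or transfusion started after a stop for any other reason as post-treatment therapy, and flag Hb and safety data collected after it.

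The cost is a few sentences in the protocol and a marker in the data. No visits, samples or subjects are added. Rescue counts may come out slightly smaller, since a subject whose anemia worsens only after stopping for another reason would be counted as post-treatment therapy.
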